Moreover, the transition from pregnancy to postpartum provides an ideal period to evaluate the utility of GWG as a potential tailoring variable. GWG is routinely documented and easily measured in all women. As such GWG would be a pragmatic variable on which to tailor treatment sequences. However, there are no data on the efficacy of GWG as a tailoring variable for perinatal weight interventions. The proposed SMART design enables us to evaluate the optimal sequence and to test the efficacy of different strategies, or combinations of sequences, for women who do and do not meet GWG goals. For example, we will compare the strategy of starting with HABITpreg and continuing with HABITpost only when GWG exceeds IOM guideline to the strategy of no treatment postpartum for women who receive HABITpreg and met their GWG goal. Alternatively, maternal weight one year postpartum may be decreased most by starting with TAU and receiving HABITpost only if GWG is high. Finally, by stratifying women according to pregravid BMI, we will be in a unique position to explore whether a different decision rule is more efficacious for a particular weight group.

There is substantial innovation in using interventions to address the different situational and psychosocial needs of women during pregnancy and the postpartum year. To date, no interventions have successfully addressed the unique sequential challenges presented by the perinatal period. We have made adaptations to the content and modality of the lifestyle interventions described, HABITpreg and HABITpost, that address conceptually relevant and modifiable factors that affect health in either pregnancy or the postpartum period. In HABITpreg, designed to address excessive GWG, we include a focus on weight stability given that weight gain is expected. In HABITpost, we recognize the increased time demands of infant care and include a focus on postpartum sleep given the impact of sleep on mood and weight in general and postpartum weight specifically, as well as the use of telephone and home visits as in our previous postpartum work.

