## **Study Objectives**

The purpose of this study is to determine the best combination of lifestyle intervention to improve maternal weight, health and psychological symptoms at 1 year postpartum.

Specific Aim 1: Determine the combination of prenatal and postpartum lifestyle interventions that optimizes maternal weight, cardiometabolic health, depressive symptoms and stress at 12-months postpartum.

Hypothesis 1: Women in HABITpreg who are assigned to HABITpost will have improved weight and secondary outcomes at 12-months postpartum relative to women who receive only HABITpreg or only HABITpost.

Hypothesis 2: Women who receive only HABITpost will have improved weight and secondary outcomes at 12-months postpartum compared to those who receive only HABITpreg or only TAUpost.

Specific Aim 2: Determine the optimal combination of interventions based on GWG that improves weight, cardiometabolic health, depressive symptoms and stress at 12-months postpartum.

Hypothesis 3: Among women who receive HABITpreg or TAUpreg and gain excessive GWG, those who are assigned to HABITpost will have improved weight and secondary outcomes at 12-months postpartum compared to those in TAUpost.

Hypothesis 4: Among women who receive HABITpost, women who met GWG goals will have improved weight and secondary outcomes compared to those who exceed GWG goals regardless of prenatal assignment.

Exploratory Aims: Evaluate the optimal sequence of interventions by prenatal weight. We will determine, for example, if the strategy of HABITpreg then HABITpost, regardless of GWG, optimizes outcomes for obese women, and if TAUpreg then HABITpost is helpful for overweight women only when GWG is excessive. Evaluate the effect of the sequence of interventions on infant risk for obesity.

Impact: This SMART is designed to identify the sequence of interventions most likely to improve maternal health at one year postpartum. Optimizing the sequence of behavioral interventions to address specific needs during pregnancy and the first postpartum year can maximize intervention potency and mitigate longer-term cardiometabolic health risks for women and their children.

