There are 8 sequences or combinations of intervention in this SMART, which we use to define group for hypothesis testing. Time also is a generic factor, and the number of levels will depend on the outcome being modeled. For example, for weight, mood and stress, time will be a linear term beginning at baseline, and a quadratic term will be added to the model if necessary. For other outcomes, time will be a factor with 4 levels (baseline, end of pregnancy, and 6- and 12-months postpartum). We also will evaluate the need to control for the effects of potential confounds such as race, age, socioeconomic status (fixed covariates) as well as breastfeeding, smoking status and physical activity (time-varying covariates). If the coefficients for groups or group by time interactions are significant, planned contrasts will evaluate groups on weight and related outcomes at 6- and 12-months postpartum. Additionally, we will create a binary variable for 5% weight loss and use generalized mixed-effect models with the logit link to compare groups on proportions with 5% loss at 6- and 12-months postpartum.

Finally, to fully utilize a SMART design, and to evaluate the utility of using GWG as a tailoring variable, we will explore what the optimal strategy is and for which participants. A dynamic strategy is a decision rule about which intervention is best initially and what intervention follows, depending on the response status. The proposed deisgn produces HABITpreg and TAU during pregnancy, and women who do and do not meet IOM guidelines for GWG each have HABITpost and TAU postpartum, resulting in the 8 possibilities sequences.

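### The plan does not say how its eight GWG-defined cells form the embedded strategies, and the one strategy comparison it spells out sets a strategy against its own met-goal branch

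*Combined protocol and SAP*

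**What the plan says.** The Statistical Considerations section takes the cell as its unit of analysis: "There are 8 sequences or combinations of intervention in this SMART, which we use to define group for hypothesis testing". It explains the count by crossing the two prenatal arms with GWG status and postpartum arm: "women who do and do not meet IOM guidelines for GWG each have HABITpost and TAU postpartum, resulting in the 8 possibilities sequences". Between these two statements it gives the definition of a dynamic strategy, "A dynamic strategy is a decision rule about which intervention is best initially and what intervention follows, depending on the response status", and says that the optimal strategy will be explored. It does not list the strategies, map cells to strategies, or name an estimator or a contrast for them.

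The Scientific Background gives a worked comparison. One side is "we will compare the strategy of starting with HABITpreg and continuing with HABITpost only when GWG exceeds IOM guideline". The other side follows directly: "to the strategy of no treatment postpartum for women who receive HABITpreg and met their GWG goal".

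Elsewhere the plan uses the terms properly. The Scientific Background describes an aim to "test the efficacy of different strategies, or combinations of sequences, for women who do and do not meet GWG goals", so there a strategy is more than one sequence. The exploratory aim in Study Objectives asks "if the strategy of HABITpreg then HABITpost, regardless of GWG, optimizes outcomes for obese women", which is a complete strategy.

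**The concern.** A strategy must say what happens to both kinds of women: those who exceed the guideline and those who do not. Each strategy therefore mixes two cells, and each woman's data bear on two strategies. A single cell holds women of one GWG status only, and that status is an outcome observed after the first randomisation. The Scientific Background itself says that excessive GWG is a strong predictor of retained weight, so cells of different GWG status are expected to differ at 12 months even if neither intervention does anything.

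The worked comparison falls into this trap. A woman on HABITpreg who meets her goal and gets no postpartum programme is already following the first strategy. The contrast sets a mixture of both kinds of women against the met-goal women alone. It therefore reflects the prognosis of excessive gainers as well as any benefit of HABITpost. Judging GWG as a tailoring variable is a stated purpose of the design, and this contrast cannot do that.

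**Working it through.** **Inputs.** The eight groups and how they arise are in Statistical Considerations. That every woman is randomised again after the T1 assessment is in Study Design & Methods, under Intervention. The share exceeding the guideline, p = 0.45 to 0.63, is from Scientific Background. The 12-month weight gap g between women who exceeded and women who met goal, absent any intervention effect, is not in the documents; I assume 1, 3 and 5 kg. The documents passed to review also give no sample size, SD or effect size.

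**Reproducing the count.** Cells: 2 prenatal arms × 2 GWG statuses × 2 postpartum arms = 8, which matches the plan. Embedded strategies: 2 prenatal arms × 2 options if excessive × 2 options if not excessive = 8. The counts coincide but the objects differ: each strategy spans 2 cells, and each cell belongs to 8 × 2 / 8 = 2 strategies.

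**The worked comparison.** Within HABITpreg, let m be the 12-month mean weight of women who met goal and received usual care postpartum. Let t be the effect of HABITpost, taken as the same in both GWG groups (negative means lower weight).

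- Tailored strategy (HABITpost only if excessive): S = (1 − p)m + p(m + g + t) = m + p(g + t)
- Its met-goal branch: B = m
- Usual care postpartum for all: T = m + pg
- HABITpost for all: A = m + pg + t

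Hence S − B = p(g + t), S − T = pt, and S − A = −(1 − p)t. Only the first contains g.

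| g (kg) | S − B, t = 0 | S − T, t = 0 | S − B, t = −1 kg | S − T, t = −1 kg |
|---|---|---|---|---|
| 1 | 0.45 to 0.63 | 0 | 0.00 | −0.45 to −0.63 |
| 3 | 1.35 to 1.89 | 0 | 0.90 to 1.26 | −0.45 to −0.63 |
| 5 | 2.25 to 3.15 | 0 | 1.80 to 2.52 | −0.45 to −0.63 |

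Ranges run over p = 0.45 to 0.63; a positive figure makes the tailored strategy look worse. With t = 0, S − A is also 0. A true 1 kg benefit of HABITpost disappears in the worked comparison when g = 1 kg and has the wrong sign when g = 3 kg or more.

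**If raw cell means were ranked.** This was simulated with no intervention effect, 10,000 runs per setting, N of 200 or 300 and SD of 6 or 8 kg (both assumed), equal allocation, and no effect of prenatal arm on GWG. The lowest-weight cell was a met-goal cell in 46 to 61% of runs at g = 0, about 70 to 90% at g = 1 kg, 96 to 99.9% at g = 3 kg, and at least 99.9% at g = 5 kg.

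**The case against.** A reader might infer that the plan mistakes its eight cells for the eight strategies and will pick a winner by ranking them, so that the search merely sorts women by GWG. The documents do not support that. They call the eight groups sequences, give no number of strategies, describe strategies as combinations of sequences, and name a complete strategy in the exploratory aim. The Scientific Background also mentions a well-formed one that starts with usual care. Nowhere does the plan say that raw cell means will be ranked, so the simulation shows only what would happen if they were. Nor does the eight-cell model block a correct analysis, because strategy means can be built from its cell means.

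A reader might also infer that the plan contains no valid evidence on tailoring. That is too strong. Since all women are randomised again, Hypothesis 3 (HABITpost against TAUpost among excessive gainers) rests on a randomised contrast and supplies part of the answer.

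A larger distortion could be claimed by setting the excessive/HABITpost cell against the met-goal/usual-care cell. With no intervention effect that gap is g itself, 1 to 5 kg. But the text names a whole strategy on the first side, so p × g is the figure that applies.

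Finally, the comparison is an illustration in the background and the strategy search is exploratory. Both are true and limit the weight of the point. But the text says that the comparison will be made, and the analysis section offers nothing to replace it.

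**Conclusion.** The point holds in this form: the plan defines a strategy correctly, gives no rule for forming strategies from GWG-defined cells, and commits to one comparison that is not between two strategies. With no intervention effect, that comparison yields about 0.5 to 3.2 kg (0.45 × 1 to 0.63 × 5), where a comparison of complete strategies yields 0. The range of p is the protocol's general range, applied here to the HABITpreg arm; g is assumed, and the protocol supports only its direction. The algebra needs no sample size or SD. Ranking raw cell means across GWG status would be confounded in the same way, but it is not a stated procedure. Hypothesis 3 is unaffected. Hypothesis 4 openly compares women by GWG status and is a separate matter. The plan should be corrected before the strategy analysis is run.

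**What to change.** List the eight strategies as prenatal arm × postpartum option if GWG is excessive × postpartum option if it is not. Estimate each 12-month mean from the planned mixed model, which keeps its handling of missing visits under MAR, as

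(1 − p̂) × (met-goal cell mean) + p̂ × (excessive cell mean),

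with p̂ the share exceeding within that prenatal arm. The standard error should reflect the estimation of p̂ and the cells that strategies share. Weighted-and-replicated regression with robust standard errors clustered by woman is an alternative. If allocation is equal at both randomisations the weights are constant and add nothing; the allocation ratio is not stated.

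Replace the comparison in the Scientific Background with two, all after HABITpreg:

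- HABITpost only if excessive versus HABITpost for all. The excessive cell cancels, leaving the met-goal contrast between HABITpost and TAUpost, scaled by 1 − p. The plan does not currently pre-state this contrast.
- HABITpost only if excessive versus TAUpost for all. The met-goal cell cancels, leaving the Hypothesis 3 contrast within the HABITpreg arm, scaled by p.

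The cost is some SAP wording and a little more analysis on data already being collected. The analysis remains exploratory.
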